## **2.3. Sample Size**

We will randomise six rehabilitation services (clusters), one in each of 6 sites, and aim to recruit 60 PWD altogether (3 services and 30 PWD to each of the intervention and the control arms). Each service will recruit 10 PWD during the 6-month recruitment period, based on a recruitment rate of 1.7 PWD per service per month as achieved during our feasibility study. If recruitment is slower than expected, we will consider adding 2 additional sites.

The sample size calculation was based on the precision for estimating the proportion of eligible people that consent to participate in the study. We anticipate that we will have to approach 150 eligible people and 40% (60 participants) of these will agree to take part. The 150 who are screened is a large enough number to estimate the percentage that consent with a 95% confidence interval 29% to 51%. If the percentage that is followed up is 80%, 60 recruited participants is large enough to estimate this with a 95% confidence interval 66% to 91%, and the 30 participants in the intervention arm is large enough to estimate the percentage that attends at least 60% of the allocated sessions with a 95% confidence interval 60% to 93%. These confidence intervals take clustering into account [3] and are based on an assumed intra-cluster (intra-service) correlation coefficient of 0.05 to quantify variability across clusters in the feasibility parameters (i.e., percentage consented, followed-up, attending at least 60% of sessions).

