## 5.2. Analysis Methods

Participant flow through the trial will be summarised using a CONSORT flow diagram for cluster randomised controlled trials.

Baseline characteristics of the services and participants will be described using means and standard deviations for continuous and count variables and numbers and percentages for categorical variables. We will report the following parameters with 95% confidence intervals that are widened to allow for clustering: % of screened people that are eligible; % of eligible people that consent to participate; % of participants that provide data at the 6-month follow-up; and % of intervention arm participants that attend at least 60% of scheduled sessions. To estimate these parameters, mixed logistic regression models with Satterthwaite's degrees of freedom correction will be fitted to binary outcomes that represent eligibility status, consent status, follow-up status and whether attended at least 60% of the scheduled sessions. The constant from these models is the log odds of the parameters which will (along with the 95% CIs) be converted to the percentage scale.

We will also report estimates of the standard deviations for continuous outcomes measured at baseline and week 28.

In order to assess the extent to which randomisation of clusters before recruiting participants may have resulted in recruitment bias due to the research nurses being unblinded, we will report the percentage of eligible people that participate in each of the intervention and control arms and examine the characteristics of the participants between the trial arms.

Finally, in ancillary analyses, we will report intention-to-treat estimates of the effect of the intervention at week 28, using 95% confidence intervals to quantify potential effectiveness. The comparison between trial arms will be undertaken by fitting mixed ("multilevel") linear regression models for continuous outcomes and mixed Poisson regression models for count outcomes; in both instances, using Satterthwaite's degrees of freedom correction to recognise the small number of clusters in the study. Comparisons will be adjusted for the baseline score of the outcome. No p-values will be reported as it is not an objective of this study to conduct a definitive test of the intervention effect.

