### 5.7. Statistical software

The latest available version of STATA at the time of analysis will be used for all trial analyses. At time of writing, this is STATA 18.5.

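### Satterthwaite degrees of freedom are promised for the logistic and Poisson mixed models with no stated way to obtain them, so small-cluster protection for the falls ratio and consent intervals is not secured

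*SAP*

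**What the plan says.** - **Feasibility percentages (SAP 5.2; same in Protocol 9.2).** Mixed logistic models with Satterthwaite's "degrees of freedom correction will be fitted to binary outcomes that represent eligibility status, consent status, follow-up status", and also to attendance at 60% or more of sessions. The model constant is back-transformed to a percentage, with a 95% interval meant to allow for clustering.
- **Arm comparisons (SAP 5.2).** Mixed linear models for continuous outcomes and "mixed Poisson regression models for count outcomes; in both instances" the Satterthwaite correction is to be used. Its stated purpose is a "degrees of freedom correction to recognise the small number of clusters in the study". Protocol 9.2 has the linear models only; the Poisson model enters in the SAP. SAP Table 16 reports falls as a rate ratio with a 95% interval.
- **Software (SAP 5.7).** "The latest available version of STATA at the time of analysis will be used for all trial analyses". No command or option is named.
- **Size (SAP 2.3).** "We will randomise six rehabilitation services (clusters), one in each of 6 sites, and aim to recruit 60 PWD altogether", three services per arm. If recruitment is slow, "we will consider adding 2 additional sites".
- **Fallback.** None is given, and SAP 5.5 rules out sensitivity analyses. Protocol 9.2 and 9.6 say the SAP will pre-specify the analyses in full.

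**The concern.** Satterthwaite degrees of freedom approximate the distribution of a contrast in a Gaussian linear mixed model. A logistic or Poisson mixed model fitted by maximum likelihood has no such quantity unless a further approximation is named, for example one based on a linearised working model. The SAP names none. For binary and count outcomes the analyst would therefore have to choose the interval at analysis, perhaps after seeing the data.

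The ordinary large-sample default is a z interval. With six services (three for attendance) it can be too narrow, and a reader of the SAP would assume that a small-cluster correction had been applied. The falls ratio carries a second exposure. A random intercept for service alone does not model differences in fall rate between people in the same service.

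**Working it through.** **1. The plan's own intervals.** Inputs from SAP 2.3: ICC 0.05; "approach 150 eligible people and 40% (60 participants) of these will agree to take part" (25 per service); 60 followed up at 80% (10 per service); 30 for attendance (10 per service). No attendance percentage is stated, so 80% is assumed.

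Design effect = 1 + (m − 1) × 0.05; effective n = n / design effect.
- Consent: 1 + 24 × 0.05 = 2.20; 150 / 2.20 = 68.2
- Follow-up: 1 + 9 × 0.05 = 1.45; 60 / 1.45 = 41.4
- Attendance: 1.45; 30 / 1.45 = 20.7

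Jeffreys intervals on these effective sizes are 29.0–51.8%, 66.0–89.9% and 59.6–92.7%. The plan states 29–51%, 66–91% and 60–93%. Every limit agrees to about one point, so the planned precision matches a large-sample calculation.

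**2. The same standard errors with few-cluster degrees of freedom.** On the logit scale SE = √(1 / (effective n × p × (1 − p))), and the limits are logit(p) ± t × SE.
- Consent: SE = √(1 / (68.2 × 0.24)) = 0.247; t on 5 df = 2.571; 26–56%
- Follow-up: SE = √(1 / (41.4 × 0.16)) = 0.389; t on 5 df; 60–92%
- Attendance: SE = √(1 / (20.7 × 0.16)) = 0.550; t on 2 df = 4.303; 27–98%

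These between-service df are an illustrative bound; Satterthwaite df could be larger. For an arm contrast with six services, t on 4 df = 2.776, and 2.776 / 1.96 = 1.42 times the z width on the log scale.

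**3. Coverage if z intervals are used: percentages.** Logit-normal service effects, maximum likelihood with 41-point quadrature, about 1,500 runs per scenario. Coverage is for the model constant.

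| Measure | ICC 0.01, z | ICC 0.05, z | ICC 0.10, z | ICC 0.05, t (services − 1) | Service variance estimated as zero, ICC 0.05 |
|---|---|---|---|---|---|
| Consent (6 × 25, 40%) | 94.3% | 90.9% | 88.6% | 97.2% | 25% |
| Follow-up (6 × 10, 80%) | 95.7% | 93.9% | 92.7% | 98.1% | 42% |
| Attendance (3 × 10, 80%) | 95.8% | 94.4% | 93.8% | 99.5% | 63% |

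The simulation error for consent is √(0.909 × 0.091 / 1500), or 0.7 points.

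**4. Coverage if z intervals are used: falls ratio.** Three services per arm with 8 followed up in each (30 × 0.8 / 3). The fall rate over follow-up and the between-service coefficient of variation (CV) are assumptions, because the documents give neither.

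| Falls per person | CV 0.1 | CV 0.25 | CV 0.5 |
|---|---|---|---|
| 1 | 95.1% | 91.9% | 86.5% |
| 2 | 93.6% | 88.3% | 81.9% |

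With added person-level gamma variation (1.5 falls, CV 0.25), z coverage is 86.2% at variance 1 and 84.1% at variance 2. Across all these scenarios, t on 4 df with the same model standard error covers 93.0–99.7%. A t interval on 4 df computed from service-level log rates covered 93–97% in separate simulations with similar assumptions. Baseline adjustment was not simulated.

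**The case against.** The strongest reply has four parts.

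- **Software.** A reader might infer that Stata cannot supply Satterthwaite df for these models, so the analysis will default to z intervals. The documents do not support that: they say nothing about what the software offers and never state that z intervals will be used. This part stands as a query to the sponsor.
- **Which measures.** A reader might infer that all the progression intervals under-cover, worst of all attendance with three services. At the plan's ICC, retention and attendance are near nominal. At ICC 0.10 simulations disagree (retention 91–93%, attendance 88–94%), so no claim is built on those values. If coverage is judged for the overall percentage and not the model constant, consent at ICC 0.05 is 92.5% and both others are 95.8%. Consent is then still short, by less.
- **Consequence.** A reader might infer that a go or stop decision is at risk. The stop/go criteria in Protocol 4.4 are thresholds on percentages, SAP Table 5 has no interval column, and the Trial Steering Committee discusses progression. The falls ratio is an ancillary analysis without p-values. No decision is shown to change.
- **Cost of a blanket t rule.** On 2 df the attendance interval is about 27–98%, too wide to inform cut-offs of 80% and 30%. This stands, and the fix does not impose it.

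None of this supplies the missing method. The instruction for binary and count models remains incomplete.

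**Conclusion.** The point holds, at moderate severity. As written, the SAP secures its few-cluster correction for the continuous outcomes only. If z intervals were used for the rest, the falls ratio interval would cover roughly 82–95%, and less for the same between-service variation once people differ in fall rate. The consent interval would cover about 91% at the plan's ICC. The falls figures rest on assumed rates and variation; with little variation between services they are close to nominal. The consent figure rests on the plan's own ICC, cluster count and denominator.

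There is a linked inconsistency. The stated precision matches a large-sample calculation, while the analysis promises a correction that could widen those intervals considerably.

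**What to change.** Amend SAP 5.2 as follows.

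- **Continuous outcomes:** keep Satterthwaite.
- **Falls:** calculate each service's log fall rate from diary falls and diary time, and compare arms with a t interval on services minus 2 df (4 with six services, 6 with eight). If baseline adjustment is kept, use baseline-adjusted service summaries and name the baseline variable, since SAP Table 16 shows no baseline row. State a rule for a service with no recorded falls.
- **Consent:** use a between-service standard error with t on services minus 1 df (5, or 7 with eight services).
- **Retention and attendance:** name the interval method actually used, say what is done when the service variance is estimated as zero, and do not call the interval Satterthwaite-corrected unless it is. For attendance, a between-service standard error with t on 2 df needs debate first. In simulation at ICC 0.05 its median interval was about 33–96%, and in about 4% of trials the three services had equal attendance, giving an interval of no width.
- **If Satterthwaite is to stay for binary or count models:** name the command, the estimation method and how the df are computed.
- **SAP 2.3:** restate the expected precision under the method chosen.

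The cost is a paragraph of SAP text and a few lines of code. The statistical price is a wider falls interval (about 1.42 times on the log scale for the same standard error) and a wider consent interval (about 26–56% against the planned 29–51%).

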### 5.3. Economic data

In order to inform data collection for an economic evaluation in the full trial, the analysis will provide descriptive statistics on the number (percentage) of completed, partially completed and non-completed health and social care resource use questionnaires including completion of individual items within the questionnaire. The analysis will also report the number (percentage) of missing scores due to incomplete individual question items for both participant and caregiver EQ-5D-5L.

### 5.4. Missing data

For all patient-reported outcome measures that have been collected, at least 90% of all questions/items must have been completed for this to be considered within the analysis. In these cases, the missing individual items will be imputed. If less than 90% of questions has been answered, the total outcome will be considered missing. For all measures, the number of participants that had data acceptable for use within the analysis will be reported.

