Quality of Life - Alzheimer's Disease (QOL-AD)	The QOL-AD is a standardised instrument for measuring quality of life for PWD [18, 19]. It is a 13-item scale administered via an interview. It includes the domains of physical condition, mood, memory, functional abilities, interpersonal relationships, ability to participate in meaningful activities, financial situation, and global assessments of self as a whole and QOL as a whole. It will be completed at baseline and 6 months by PWD with the capacity to complete the items.  Points are assigned to each item as follows: poor (1), fair (2), good (3), and excellent (4).  The total score is the sum of all 13 items.	Baseline, 6 months
International short form Falls Efficiency Scale (Short-FES-I)	The psychological consequences of falling will be determined using the Short-FES-I [20]. This is a 7-item measure of falls efficacy (or fear of falling). It will be completed at baseline and 6 months by PWD with the capacity to complete the items.  Points are assigned to each item as follows: not at	Baseline, 6 months
	all concerned (1), somewhat concerned (2), fairly concerned (3), and very concerned (4).  To calculate the Short FES-I score when all items are completed, simply add the scores for each item together to give a total that ranges as follows:	
	Short FES-I: minimum 7 (no concern about falling) to maximum 28 (severe concern about falling)	
	Scoring with missing items	
Time delle and On tool	If responses are missing on more than four items on more than two items (i.e.≥3) for Short-FES-I then the questionnaire scores cannot be used. If responses are missing on 2 or less on Short FES-I then it is possible to calculate a Short FES-I score. To do this first calculate the total score of the items which have been completed. Divide that score by the number of items completed and then multiply by 7. The new total score should be rounded up to the nearest whole number to give the score for an individual. For example, if scores on Short FES-I were: Item 1=2 Item 2=3 Item 3=missing Item 4=3 Item 5=2 Item 6=4 Item 7=missing Then 2+3+3+2+4=14/5 = 2.8×7= 19.6 which is rounded up to 20.	Describes
Timed Up and Go test	Patient participants stand up and walk 3 metres, turn around and walk back. The time taken to complete it is recorded. The test is scored as time in seconds.	Baseline, 6 months
	10 seconds or less = normal	
	10 to 20 seconds = good mobility	
	20 to 30 seconds = problems with mobility	

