### 9.5. Procedure(s) to account for missing or spurious data

Every attempt will be made to collect a complete record of data during the trial, with queries being raised for missing data to collect these within a reasonable time window if available. All data that are missing should be appropriately coded with the reason, if known, for why the data is missing.

Missing data will not be imputed for analysis. Complete case analyses of the outcome will be undertaken when comparing them between trial arms.

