#### **3.3. Analysis populations**

For all analysis of outcome measures within this trial, an intention-to-treat approach will be implemented, except for analysis of safety and harms data, where an as-treated approach will be used. For a participant to be included within the safety population data, they must have received at least one intervention session to be considered within the intervention group for analysis.

Data for these analyses will use observed data only, with no use of imputation planned as part of the analysis.

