### **5. Statistical Analysis**

#### **5.1. Outcome definitions**

Feasibility Outcomes that will determine whether to proceed to full trial are as follows:

- Proportion of eligible patients consenting to pilot trial
- Proportion of participants that attend  $\geq 60\%$  of sessions as planned
- Proportion of consented participants that provide key outcome data at week 28

Pilot Randomised Controlled Outcomes are as follows:

- Activities of daily living (ADL) assessed with the Disability Assessment for Dementia (DAD) at Baseline and 28 Weeks
- European Quality of Life Instrument (EQ-5D-5L) at Baseline and 28 Weeks
- Quality of Life - Alzheimer's Disease (QOL-AD) at Baseline and 28 Weeks
- International short form Falls Efficiency Scale (Short-FES-I) at Baseline and 28 Weeks
- Timed Up and Go test at Baseline and 28 Weeks
- Goal Attainment Scaling (GAS) (intervention only) at Baseline, 12 Weeks and 28 Weeks
- Cognition assessed with Mini-ACE at Baseline
- Falls Diary assessed during the 6 months of follow up
- Carer burden assessed with the Zarit burden interview 12 (ZBI-12) at Baseline and 28 Weeks
- Carer participant quality of life assessed with the European Quality of Life Instrument (EQ-5D-5L) at Baseline and 28 Weeks
- Carer rated Patient participant quality of life assessed with the EQ-5D-5L proxy at Baseline and 28 Weeks
- Carer rated patient participant quality of life QoL-AD Proxy at Baseline and 28 Weeks
- Health and social care Utilisation Questionnaire (HUQ) at Baseline, 12 Weeks and 28 Weeks

Methods of calculation for all outcomes are defined within the protocol in Table 2.

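### SAP 5.4's 90%-of-items rule voids Short-FES-I scores that protocol Table 2, adopted by SAP 5.1, would keep and pro-rate

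*SAP*

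**What the plan says.** SAP 5.4 sets one completeness threshold for all patient-reported measures: "at least 90% of all questions/items must have been completed for this to be considered within the analysis". Below it, the score is lost: "If less than 90% of questions has been answered, the total outcome will be considered missing". At or above it, any gaps are filled: "In these cases, the missing individual items will be imputed". No method is named. The section also undertakes to report how many participants had usable data on each measure.

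SAP 5.1 points elsewhere for scoring: "Methods of calculation for all outcomes are defined within the protocol in Table 2". In that table (protocol 4.5), the seven-item Short-FES-I has its own missing-item rule: "If responses are missing on 2 or less on Short FES-I then it is possible to calculate a Short FES-I score". The score is the mean of the answered items multiplied by seven and rounded up. A worked example with two blanks is given.

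On imputation in general, SAP 3.3 describes an observed-data analysis "with no use of imputation planned as part of the analysis", and protocol 9.5 says "Missing data will not be imputed for analysis", followed by a commitment to complete-case analysis of the outcome. SAP 5.5 plans no sensitivity analyses.

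**The concern.** For a Short-FES-I form with one or two blanks, SAP 5.1 (through Table 2) gives a score and SAP 5.4 gives a missing value. The SAP does not say which governs, so two analysts following it faithfully could arrive at different analysis sets.

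If SAP 5.4 is followed, three outputs are affected. The count of usable Short-FES-I data comes out too low, in a pilot whose purpose is to learn what can be collected. The standard deviations reported under SAP 5.2 rest on fewer people. The exploratory between-arm difference loses precision, the more so because it is adjusted for baseline and a form voided at either visit removes the participant. With no sensitivity analysis planned, nothing in the output would show that the rule was responsible.

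The unnamed item imputation is a different matter. It keeps forms rather than losing them, but the scores it produces cannot be reproduced from the SAP.

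**Working it through.** **Table 2's own example.** Five items are answered: 2, 3, 3, 2 and 4, which sum to 14. Then 14/5 = 2.8, and 2.8 × 7 = 19.6, rounded up to 20. This matches the protocol. Completeness is 5/7 = 71.4%, so SAP 5.4 treats the same form as missing.

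**What 90% means for each scale.** A scale of k items with m blanks passes if (k − m)/k ≥ 0.90. Item counts are from protocol Table 2; the five EQ-5D-5L domains are implied by the instrument's name.

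| Scale | Items | Most blanks allowed by SAP 5.4 | First failing case | Rule in Table 2 |
|---|---|---|---|---|
| Short-FES-I | 7 | 0 | 6/7 = 85.7% | up to 2 blanks, pro-rated |
| EQ-5D-5L | 5 | 0 | 4/5 = 80% | none stated |
| ZBI-12 | 12 | 1 | 10/12 = 83.3% | none stated |
| QOL-AD | 13 | 1 | 11/13 = 84.6% | none stated |
| DAD | 40 | 4 | 35/40 = 87.5% | N/A items leave the denominator; nothing on blanks |

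The direct conflict is confined to the Short-FES-I. For that scale 0.90 × 7 = 6.3, so all seven items are needed and SAP 5.4's item imputation can never operate.

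**Size, under an assumption.** The documents give no item non-response rate. Let each item be blank independently with probability q.

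- Usable under SAP 5.4: (1 − q)^7.
- Usable under Table 2: P(at most 2 blanks of 7), binomial.
- Base: 60 recruited × 80% followed up (the planning figures in protocol 9.1 and SAP 2.3) = 48.

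| q | SAP 5.4 | Table 2 | Scores lost at one visit, of 48 |
|---|---|---|---|
| 2% | 0.868 | 0.9997 | 48 × 0.132 = 6.3 |
| 3% | 0.808 | 0.9991 | 48 × 0.191 = 9.2 |
| 5% | 0.698 | 0.9962 | 48 × 0.298 = 14.3 |

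**Effect of clustering.** At q = 5%, the expected number of blank items is 0.05 × 7 × 48 = 16.8. If they all fell in pairs, 16.8/2 = 8.4 forms would be affected instead of 14.3. If they all fell in forms with three or more blanks, both rules would void those forms and the difference would be zero. The tabled figures are therefore an illustration under independence, not a forecast.

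**The case against.** The strongest reply is that little hangs on this. The Short-FES-I is a secondary outcome, the arm comparison is ancillary, and no p-values are reported. The quantitative progression criteria concern consent, attendance and retention for key outcome data, and neither document names the Short-FES-I as key outcome data or bases the sample size on it. That stands, and it limits the severity.

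Item non-response may also be low. Researchers collect the measures at visits, the electronic forms query missing data (protocol 9.5 and 10.1), and protocol section 2 reports that outcome measurements were successfully collected when the intervention was tested in 11 people. That is fair, and it is why the loss is given only as an assumed range. It does not tell the analyst which rule to apply when a blank occurs.

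Three stronger readings are tempting, and the documents do not support them.

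- **The DAD is at risk.** A reader might infer that five N/A items (35/40 = 87.5%) would void the measure that Table 2 lists as primary. Table 2 lists N/A among the ways of scoring an item and removes it from the denominator, so N/A is most naturally a completed response. The DAD is also completed by the carer, so it is not clear that a rule for patient-reported measures reaches it. One sentence of confirmation is enough.
- **The imputation statements are a flat contradiction that costs data.** Protocol 9.5 goes on to complete-case analysis of the outcome, and the same protocol pro-rates items in Table 2. Its statement is therefore best read as being about wholly missing outcomes. SAP 3.3 can be read the same way. Neither says so, which is the gap, but no data are lost through it.
- **The 90% rule is wrong for every scale.** For QOL-AD and ZBI-12 it allows one blank and for EQ-5D-5L none, and Table 2 sets no different missing-item rule for these scales.

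Last, the SAP cites protocol version 5.0, whereas the version reviewed is 3.0. Table 2 or section 9.5 may have changed in between, and that could not be checked.

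**Conclusion.** The conflict is real and follows from the text: one or two blanks on the Short-FES-I give a score under Table 2 and SAP 5.1, and a missing value under SAP 5.4. Applying SAP 5.4 would discard usable secondary-outcome data and understate completeness for that scale. The loss would be about 6, 9 or 14 of 48 scores at one visit if item non-response were 2%, 3% or 5% and independent, and smaller if blanks cluster. Those rates are assumptions. The conflict itself does not depend on them, but it does depend on Table 2 being unchanged in protocol version 5.0.

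The unnamed imputation method is a separate point of reproducibility and scope. Severity overall is minor to moderate: worth settling before the analysis starts, so that the choice of rule cannot be influenced by the data, but no threat to the progression decision or the sample size.

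**What to change.** 1. In SAP 5.4, state that instrument-specific missing-item rules in protocol Table 2 take precedence (Short-FES-I: two or fewer blanks, pro-rated) and that the 90% rule applies only to scales without a rule of their own.
2. Name the item-level imputation method for those remaining scales.
3. Confirm that N/A on the DAD is a valid response, excluded from the denominator and not counted as a blank.
4. Reword SAP 3.3 to say that wholly missing outcome scores will not be imputed, and align protocol 9.5 at the next amendment.
5. Check Table 2 and section 9.5 in protocol version 5.0 before finalising the wording.

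The cost is a short SAP revision, plus one sentence in the protocol that can wait for an amendment made for other reasons. No data collection changes.
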